7.0 Data and Specimen Banking*

Data Storage: Online questionnaire data will be housed behind a secure firewall on the NCH research internet server. Electronic recordings will be stored on NCH computers. Data collected on paper will be entered into electronic study databases and original files will be kept in a locked cabinet within a locked office at the hospital. Only direct study personnel will have access to this information.

Data Description: Data described in Section 6.0 will be collected for each participant.

Data Sharing: It is NIH policy that the results and accomplishments of the activities that it funds should be made available to the public (see https://grants.nih.gov/policy/sharing.htm). If data are shared, the PI will ensure all mechanisms used to share data will include proper plans and safeguards for the protection of privacy, confidentiality, and security for data dissemination and reuse (e.g., all data will be thoroughly de-identified and will not be traceable to a specific study participant). Plans for archiving and long-term

preservation of the data will be implemented, as appropriate. In addition, this study will be conducted in accordance with the following publication and data sharing policies and regulations:

- National Institutes of Health (NIH) Public Access Policy, which ensures that the public has access to the published results of NIH funded research. It requires scientists to submit final peer-reviewed journal manuscripts that arise from NIH funds to the digital archive PubMed Central upon acceptance for publication.
- This study will comply with the NIH Data Sharing Policy and Policy on the Dissemination of NIH-Funded Clinical Trial Information and the Clinical Trials Registration and Results Information Submission rule. As such, this trial will be registered at ClinicalTrials.gov, and results information from this trial will be submitted to ClinicalTrials.gov. In addition, every attempt will be made to publish results in peer-reviewed journals.

8.0 Sharing of Results with Subjects*

Individual subject results will not be shared directly with participants. Overall study results may be shared with participants via study newsletters or similar.

9.0 Study Timelines*

Participants will be enrolled in this study for approximately 1 year.

We expect it will take 48 months to enroll all participants and that the primary analysis will be completed within one year after enrollment is completed.

10.0 Inclusion and Exclusion Criteria*

Eligibility: After an initial and new cancer diagnosis, an automatic referral is placed for a fertility consult and [name] is immediately notified of the age and sex of the patient. The patient and family then consult with a fertility navigator to discuss fertility options, per standard of care. During the fertility consult the fertility navigator will assess pubertal status/eligibility for sperm banking, provide verbal and written information about infertility risk and FP options (masturbation/sperm extraction), and then introduce the study. The patient's eligibility is communicated to study staff. If the participant is eligible, study staff will approach the family for recruitment purposes.

Inclusion Criteria: Child participants must meet all the inclusion criteria to be eligible for the study. The inclusion criteria are:

- Male
- Aged 12-25 years
- Expected to have adjuvant therapy (chemotherapy and/or gonadal radiation) for newly diagnosed cancer
- Pubertal (at least Tanner stage 2-3, eligible for sperm banking as determined in the fertility consult)
- Proficient in English

Primary caregivers of eligible children are also invited to participate if they have participated in the fertility consult. These caregivers may include biological parents, adoptive patterns, other primary caregivers (e.g. grandparents), or same sex parents.

Exclusion Criteria: Child participants meeting any of the exclusion criteria at baseline will be excluded from the study. The exclusion criteria are:

- Cognitive deficit that precludes completing measures
- Parents are non-English speaking

11.0 Vulnerable Populations*

This study will include children who have not obtained the legal age to consent. The following safeguards will be followed to protect their rights and welfare: study staff will not approach without at least one parent present, staff will make it clear that if the child feels overwhelmed or uncomfortable they may stop participating at any time, and, when appropriate, staff may approach parents separately from the child to ensure that child is able to complete study measures.

12.0 Local Number of Subjects

This study will enroll 40 male AYAs and 70 caregivers, at the single-site, Nationwide Children's Hospital. There are approximately 30 males newly diagnosed with cancer in our target age range each year. Taking into account our inclusion/exclusion criteria, infrastructure of the fertility consult service, and recruitment rates in our pilot (>90%), we anticipate completing our recruitment goals within the allocated timeframe.

13.0 Recruitment Methods

At Nationwide Children's Hospital (NCH), every patient with a new cancer diagnosis has an automatic referral placed to the multidisciplinary Fertility and Reproductive Health Team. The oncofertility navigator meets with the patient and family to assess pubertal status and achievement of sexual milestones (masturbation), review infertility risk, present FP options, and discuss logistics (including cost). After the oncofertility navigator completes the consult and introduces the study to the family, the study team will approach those who are eligible and invite their participation. Study staff will primarily recruit in person, in clinic. As the first assessment will occur immediately after the fertility consult (before cancer treatment), most AYA have two parents present. If participants are unavailable at times of appointments or admissions, study staff may contact families via telephone or email.

If a participant is not present during the time of in person recruitment, but is available remotely, study staff will obtain contact information from the present participants and will initiate a phone call. The study staff will then go through recruitment with the participant over the phone or via Webex.

- *Incentives:* Families will receive the following incentives for their participation (participants approached in person will receive their incentive at the conclusion of a visit. Participants approached remotely will receive incentives via mail):
 - Baseline: \$10 ClinCard for each participant
 - 1-month follow-up: \$20 ClinCard for each participant
 - 1-year follow-up: \$30 ClinCard for each participant

Retention: Based on our previous work, engagement at 1-month post intervention is 100% due to patients actively being on treatment for their cancer diagnosis, routine clinical follow-up appointments, and other treatment-related in and outpatient encounters taking place at Nationwide Children's Hospital. Therefore, we anticipate similarly high retention in this study. However, additional strategies will be used to keep families engaged throughout the study, including the 1-year post-intervention follow up. These include:

- Coordinating follow-up appointments with already scheduled clinic visits
- Routine correspondence with their medical team, and checks of the NCH electronic medical record for updated contact information or upcoming appointments within the hospital
- Check-in phone calls, emails, and/or text messages

14.0 Withdrawal of Subjects*

Participants may be withdrawn if the intervention causes distress and it is determined by the interventionist and/or medical team that is not in the participant's best interest to continue. If the participant withdrawals from the intervention, study staff will encourage completion of study data collection, per intent-to-treat methodology.

15.0 Risks to Subjects*

It is expected that completing study questionnaires and interviews will introduce minimal risk to participants, yet the study team acknowledges that the new cancer diagnosis will be a stressor for AYAs and parents. Participants may experience some discomfort and/or embarrassment when completing survey items or interviews about FP. Given the study design, all patients and caregivers will have already received information about FP during the clinical fertility consult, per standard of care. Parents or AYAs may experience distress when asked about parent-child communication, although we do not expect this to have severe or long-lasting effects on the respondent. In preliminary work, parents and AYA have completed measures, similar to those in this study, within 10 minutes and provided positive feedback about the experience, emphasizing their perceived importance of addressing this topic. Loss of confidentiality is also a potential risk, although no more so than in any other research study. The study team will take every precaution to prevent this.

16.0 Potential Benefits to Subjects*

Participants may or may not receive direct benefits from participating in this study. Questionnaires may help patients and families make FP decisions and the family-centered, psychoeducational decision tool may increase caregiver/child communication. This study also has strong potential to improve care for other AYA with cancer and their families, by optimizing FP rates and decision quality.

17.0 Data Management* and Confidentiality

Data Collection & Management: Data collection will be the responsibility of the study staff under the supervision of the PI. The PI will be responsible for ensuring the accuracy, completeness, legibility, and timeliness of the data reported.

All source documents will be completed in a neat, legible manner to ensure accurate interpretation of data. Hardcopies of the study visit worksheets will be provided for use as source document worksheets for recording data for each participant consented/enrolled in the study. Data recorded in the electronic case report form (eCRF) derived from source documents will be consistent with the data recorded on the source documents.

Clinical data (including AEs) and clinical laboratory data will be entered into secure study databases, if needed. The data system includes password protection and internal quality checks, such as automatic range checks, to identify data that appear inconsistent, incomplete, or inaccurate. Clinical data will be entered directly from the source documents.

Only authorized study staff will have access to study data.

Sample Size Determination: The sample was determined based on the medium-large effects found in our previous work and work by Klosky et al. and is sufficient to find similar sized effects; thus our proposed sample size will enable us to detect effect sizes previously found in the literature^{26,54-56}.

A sample size of n=20 per group will provide 80% power to detect large effect sizes of w=.45 for the chisquare analysis and d=.91 for the independent samples t-test. Because this is a pilot study, the focus will be on generating reliable effect size estimates for our primary outcome (FP uptake) comparing the intervention to standard care, rather than on statistical significance (using two-sided type I error rates (alpha values) of no more than .05). The proposed sample size is sufficient for gleaning this information.

Data Analysis Plan: Analyses will be conducted according to intent-to-treat methods, in which all randomized participants are included. Summary statistics will be calculated and qualitative methods used to evaluate the feasibility of recruiting and enrolling children.

Chi-squared and t-tests will be used to evaluate primary and secondary outcomes. A chi-square analyses will examine the primary outcome of FP uptake (Y/N) as a function of treatment group status An independent samples t-test will examine whether the secondary outcomes of decision quality (numerical score on the BSDQ and family communication (numerical score on the PACS and difference scores on the PACS for AYA and parents) change between 1-month and 1-year follow-ups. Pearson's r correlations will be run to see if FP uptake (Y/N) is related to decision quality or family communication.

The two groups (intervention and control) will be examined in an *exploratory* manner to assess potential differences in factors known to affect FP decisions such as demographics (e.g. age), urgency to start treatment, knowledge, provider recommendation, and parent recommendation, as well as novel factors such as quality of parent-child communication. We will also examine these baseline factors as covariates within an analysis of covariance to see if might have a substantial impact on our effect size estimates for the larger RCT.

Quality Control of Data: Internal quality management of study conduct, data collection, documentation and completion will be conducted, under the direction of the PI. Quality control (QC) procedures will be implemented as follows:

- Informed consent: Study staff will review both the documentation of the consenting process as well as a percentage of the completed consent documents. This review will evaluate compliance with GCP, accuracy, and completeness. Feedback will be provided to the study team to ensure proper consenting procedures are followed.
- Source documents and the electronic data: Some data will be initially captured on source documents and will ultimately be entered into the study database. Some data will be entered directly into an electronic data capture system. To ensure accuracy of data initially captured on source documents, site staff will compare a representative sample of source data against the database, targeting key data points in that review. Some data will be entered directly into study databases. Electronic databases will be programed to alter study staff and/or participants of out of range values and/or potential errors.
- Protocol Deviations: The study team will review protocol deviations on an ongoing basis and will implement corrective actions when the quantity or nature of deviations are deemed to be at a level of concern. This protocol defines a protocol deviation as any noncompliance with the clinical trial protocol, International Council on Harmonization Good Clinical Practice (ICH GCP), or Manual of Procedures (MOP) requirements. The noncompliance may be either on the part of the participant, the investigator, or the study site staff. As a result of deviations, corrective actions will be developed by the site and implemented promptly, if needed. These practices are consistent with ICH GCP:
 - Section 4.5 Compliance with Protocol, subsections 4.5.1, 4.5.2, and 4.5.3
 - Section 5.1 Quality Assurance and Quality Control, subsection 5.1.1
 - Section 5.20 Noncompliance, subsections 5.20.1, and 5.20.2.

It is the responsibility of the PI to use continuous vigilance to identify and report deviations as required by the IRB and the funder, as well as oversee quality control of data. The site investigator is responsible for knowing and adhering to the reviewing IRB requirements. Should independent monitoring become necessary, the PI will provide direct access to all trial related sites, source data/documents, and reports for the purpose of monitoring and auditing by the funding agency, and inspection by local and regulatory authorities.

Handling of Data: The following data will be collected for each participant

- Demographics (e.g. age, race, ethnicity).
- Medical information (e.g. cancer type, treatment levels, infertility risk), collected via medical chart review.
- Information about decision and FP-related thoughts and feelings, collected via decision tool, parenthood goals surveys, and intervention.
- Participant report of communication with son or parents, collected via PACS survey.
- Participant report of decision satisfaction, collected via BSDQ.
- Participant report of feasibility and acceptability of participation in research.
- Open-ended interviews, recorded and transcribed verbatim. These interviews will focus on how participants made their decision, how they feel about their decision, alternatives they had considered, more information or support they would like to have had prior to their decision, what they would find helpful moving forward related to their fertility and future parenthood, and how participating in the study impacted them.

Study participant research data, which is for purposes of statistical analysis and scientific reporting, will be collected and maintained in REDCap, a secure electronic data capture system on the NCH research internet server. Some data may be collected on paper and will be entered into REDCap. Individual participants and their research data will be identified by a unique study identification number. Other types of data (e.g., audio recordings from the interviews and intervention) may be kept in a locked cabinet within a locked office at the hospital or on an NCH computer. Only direct study personnel will have access to this information. The study data entry, study management systems, and related study files will be secured and password protected.

Study documents will be retained for a minimum of 2 years after the formal discontinuation of clinical development of the study intervention. These documents will be retained for a longer period, if require by local regulations.

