Aims: This randomized clinical trial (RCT) will test the feasibility, acceptability, and preliminary efficacy of a novel family-centered, psychoeducational intervention with known and newly identified factors to improve fertility preservation (FP) uptake, decision quality, and family communication among male adolescents and young adults (AYAs) newly diagnosed with cancer. The primary aim of this project is to examine preliminary efficacy of the psychoeducational intervention with regard to FP uptake.

Hypotheses: The primary hypothesis is that compared to standard of care control group (routine fertility consult at diagnosis, n=20), AYAs in the intervention arm (routine fertility consult at diagnosis + FP Decision Tool and Facilitated Conversation by trained interventionist; n=20) will have higher rates of FP uptake. The secondary hypotheses are that families in the intervention group will report better FP decision quality and report improvements in family communication, compared to those in the control arm.

Rationale: Nearly 9,000 males under age 20 are diagnosed with cancer in the U.S. each year¹. With 5-year survival rates exceeding 80%, the population of male childhood cancer survivors is now close to 200,000². Unfortunately, approximately 50% of male survivors have impaired fertility³⁻⁵, which can impede psychosexual development and diminish quality of life (QoL)⁶. Sperm banking is an established and effective method of FP for pubertal males⁷, yet only 25% of eligible adolescents bank sperm prior to

treatment⁸⁻¹². As these AYAs complete therapy and approach their reproductive years, many survivors and their parents *regret* missed opportunities for FP and report *distress* about potential infertility¹³⁻¹⁶.

Significant knowledge gaps exist with regard to pediatric FP:

- 1. Most research examining FP decisions has focused on females^{17,18}, despite a higher prevalence of cancer and treatment-related infertility in males¹⁹;
- 2. Many studies examining FP predictors have been conducted years after therapy and are subject to recall bias^{15,20};
- 3. Little attention has been paid to *decision quality* (satisfaction/regret) soon after FP decisions are made;
- 4. Although parents make most healthcare decisions even in late adolescence/young adulthood, *family factors* including parent-child communication about FP, have not been examined.

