FP interventions have primarily focused on patient-provider communication and increasing knowledge²¹⁻ ²³, but in a recent study, half of 13-21-year old males who were told they were at risk for infertility still declined FP before treatment²⁴. Notably, *parents' recommendation to bank* was one of the strongest predictors of FP^{25,26}. However, research has shown that parents do not prioritize fertility in the setting of their child's new cancer diagnosis^{27,28}. AYA survivors and parents in our recent pilot study had discordant attitudes about FP, with parents significantly underestimating the impact of potential infertility on their sons. Thus, knowledge is critical, but other *individual and family* factors must be identified to explain gaps between those pursue and decline FP. The relative ease but underutilization of sperm banking, as well as the psychosocial implications of infertility, demonstrate a need for novel family-centered interventions at the time of diagnosis to optimize FP uptake and decision quality for this unique and vulnerable population^{25,26}. Such interventions have improved parent-child communication about sexual health topics and have shown promise in other conditions such as multiple sclerosis. However, research at the time of diagnosis has been limited by concerns that the burden of participating could be too heavy at such a tumultuous time. Previous research has shown that participating in FP focused research at the time of diagnosis is rated as beneficial or neutral by AYAs and families²⁹. In our ongoing observational pilot (IRB17-00883) our recruitment rate is 93% for Visit 1 and 81% for Visit 2, which shows that a study of this kind is feasible at the time of diagnosis.

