3.0 Background

A rapidly growing population of male childhood cancer survivors are at risk for infertility and distress. As the number of male cancer survivors rises, it is essential to minimize treatment late effects^{2,30}. One of the most prevalent and significant complications among males is infertility^{3-5,30,31}, which can impair psychosocial development and reduce quality of life⁶. National guidelines emphasize offering fertility preservation (FP) prior to initiation of cancer therapy³², and sperm cryopreservation is an established and generally noninvasive FP method for pubertal males. Early research suggested only males receiving high doses of alkylating agents should bank sperm³³. However, variable sperm counts following equivalent doses of cyclophosphamide and scenarios in which patients have to move quickly from "low risk" treatments (which transiently impair sperm production) to "high risk" treatments, support the premise that all males receiving chemotherapy and/or gonadal radiation should consider FP at diagnosis^{3,5,32,34}. Despite studies showing ~50% of male childhood cancer survivors have fertility impairment^{3,4,33,35}, reports from many centers show only ~25% of pubertal males bank sperm prior to treatment⁸⁻¹². As survivors enter their reproductive years, many regret missed opportunities for FP and experience *distress* about potential infertility^{11,13-16,36}. Thus, interventions to improve FP uptake would have great potential for reproductive and psychological benefit.

Individual and family factors associated with sperm banking decisions remain poorly understood. Young age, cost, inadequate knowledge, and urgency to start treatment are common barriers to FP among AYA males with newly diagnosed cancer^{9,37-40}. As a result, most fertility counseling and FP interventions have targeted healthcare providers and systems or provider-patient interactions^{21-23,41}. While these are critical factors, less than half of male AYA advised

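### The plan calls 20 per arm sufficient for reliable estimates of the FP-uptake effect, but supports this only with power and plans no confidence interval; the 95% half-width would be about 24 to 28 percentage points

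*Combined protocol and SAP*

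**What the plan says.** Section 17.0, Sample Size Determination, gives one figure for the primary outcome: "n=20 per group will provide 80% power to detect large effect sizes of w=.45". It then turns from testing to estimation. Because the study is a pilot, "the focus will be on generating reliable effect size estimates for our primary outcome (FP uptake) comparing the intervention to standard care", in preference to statistical significance. The paragraph closes: "The proposed sample size is sufficient for gleaning this information". No interval width or other precision figure is given.

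Section 17.0, Data Analysis Plan, states the primary analysis: "A chi-square analyses will examine the primary outcome of FP uptake (Y/N) as a function of treatment group status". It does not say that a risk difference, a risk ratio, an odds ratio or w itself will be reported for uptake. No confidence interval is named anywhere in the document. Effect sizes come up once more, in the exploratory covariate analysis, which asks whether baseline factors might have a "substantial impact on our effect size estimates for the larger RCT".

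The document gives no planning rate for either arm. It does cite background rates. Section 2.0, Rationale: "yet only 25% of eligible adolescents bank sperm". Section 3.0: "reports from many centers show only ~25% of pubertal males bank sperm prior to" treatment. Section 2.0 also says of a recent study that "half of 13-21-year old males who were told they were at risk for infertility still declined FP".

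**The concern.** When estimation is the declared purpose, the sample size should be judged by how precisely it estimates the effect, and the analysis should report the estimate with its uncertainty. Here the justification and the primary analysis are both about a test. The power statement does not show whether the uptake effect will be known to within 5 points or 30, so the sufficiency claim has no numerical support.

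What is at stake is how the pilot will be read. A chi-square p-value, or a bare point estimate, would not show how little 20 families per arm pin down the effect, and the document expects effect sizes to inform a larger trial. If no effect measure is named in advance, the choice between a difference, a ratio and an odds ratio also stays open until the data are in.

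**Working it through.** **1. The plan's own figure.** Inputs from Section 17.0: 20 per arm (N = 40), w = .45, two-sided alpha .05. For a 1-df chi-square test the noncentrality is N·w² = 40 × 0.45² = 8.1, and the power is 81.2%. The stated 80% reproduces.

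**2. What w = .45 means in uptake.** For equal arms, w = |p₂ − p₁| / (2√(p̄(1 − p̄))), where p̄ is the mean of the two rates.
- 25% versus 70%: p̄ = 0.475, w = 0.45/(2 × 0.4994) = 0.45.
- 50% versus 91%: p̄ = 0.705, w = 0.41/(2 × 0.4560) = 0.45.

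The detectable effect is therefore a gain of about 41 to 45 points. The plan does not translate it this way.

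**3. Inputs for precision.** Control uptake of 25% to 50% is an assumption taken from the background rates in Sections 2.0 and 3.0. Gains of 0 to 45 points are also an assumption, so the intervention arm goes up to 95%.

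**4. Interval.** The Newcombe method combines the Wilson limits (l, u) of each arm. With d = p₂ − p₁ (intervention minus control):
- lower limit = d − √[(p₂ − l₂)² + (u₁ − p₁)²]
- upper limit = d + √[(u₂ − p₂)² + (p₁ − l₁)²]

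Worked case, 10/20 versus 5/20. The Wilson limits are 0.299 to 0.701 for 10/20 and 0.112 to 0.469 for 5/20.
- Lower: 0.25 − √(0.2007² + 0.2187²) = 0.25 − 0.297 = −0.047
- Upper: 0.25 + √(0.2007² + 0.1381²) = 0.25 + 0.244 = 0.494
- Half-width: (0.494 + 0.047)/2 = 0.270

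**5. Range at 20 per arm.**

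| Intervention vs control | Difference (points) | 95% Newcombe CI | Half-width |
|---|---|---|---|
| 5/20 vs 5/20 | 0 | −25.9 to +25.9 | 25.9 |
| 10/20 vs 5/20 | +25 | −4.7 to +49.4 | 27.0 |
| 14/20 vs 5/20 | +45 | +14.1 to +65.7 | 25.8 |
| 10/20 vs 10/20 | 0 | −28.4 to +28.4 | 28.4 |
| 18/20 vs 10/20 | +40 | +11.6 to +61.3 | 24.9 |
| 19/20 vs 10/20 | +45 | +17.6 to +65.5 | 23.9 |

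Over all counts with control 5 to 10 of 20 and a gain of 0 to 9 of 20, the half-width runs from 23.9 (19/20 vs 10/20) to 28.4 (10/20 vs 10/20). Wald intervals over the same counts run from 23.9 to 31.0. Larger gains give narrower intervals: 18/20 vs 6/20 gives 23.4 and 18/20 vs 5/20 gives 22.6.

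**6. Choice of interval.** Exact coverage was enumerated at six true rate pairs (25% control with 25%, 50% or 70%; 50% control with 50%, 75% or 90%). Newcombe stays at about 95%, while Wald covers about 92% to 94%.

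**7. What the width means for a later trial (illustration only; the plan gives no sizing rule).** With control 25%, 80% power and two-sided .05, n per arm = [1.96√(2p̄(1 − p̄)) + 0.8416√(p₁(1 − p₁) + p₂(1 − p₂))]² / (p₂ − p₁)². For 50% this is (1.342 + 0.557)²/0.0625, or 58. It is 329 for 35% and 24 for 65%. All three gains (+25, +10, +40) lie inside the single interval for 10/20 versus 5/20.

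**The case against.** The strongest reply is that this is a pilot and says so. The document speaks of preliminary efficacy throughout and sets no precision target, so there is no internal standard that a 24 to 28 point half-width fails. Wide intervals are normal at 20 per arm. Anyone given the two-by-two counts can compute the interval.

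Much of this stands, and it limits the point. A reader might infer that the power calculation is wrong, or that two figures in the plan contradict each other. Neither is so: the power reproduces, and the fault is an unquantified claim. A reader might also infer that the sponsor will size the larger trial on the point estimate alone. No section says that; the one mention of the larger trial sits in an exploratory covariate check. Nor do the documents support the view that the trial must enrol more families, since nothing in them requires a given precision.

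The rates deserve caution too. The 25% and 50% are background literature rates. In this trial every patient has an automatic referral and a navigator consult, and no local uptake rate is given. Section 3.0 puts banking among those advised in a recent study at less than half, so 50% is an upper reading of that source. Newcombe and the risk difference are reasonable choices, not the only ones.

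The reply does not rescue the sufficiency claim. The plan uses pilot status as its reason for putting estimation first, which makes precision the relevant criterion. That an interval could be computed afterwards is no substitute for naming the effect measure and interval in advance.

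**Conclusion.** The point holds as a gap between the stated purpose and its support. Section 17.0 makes reliable estimation of the uptake effect the focus and declares 20 per arm enough, but offers only power as evidence, plans only a chi-square test for uptake, and plans no confidence interval. With observed control uptake of 25% to 50% and gains of 0 to 45 points, both assumed, the 95% Newcombe half-width is about 24 to 28 points, and somewhat less for larger gains. An observed gain of 25 points from 25% would be compatible with a small loss or with a gain of nearly 50 points. That does not support calling the estimate reliable or the sample sufficient for it. The change is worth making because it concerns the primary outcome and the pilot's declared focus. It corrects a claim and an omission in the analysis plan; the stated power figure stays as it is.

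**What to change.** 1. Section 17.0, Data Analysis Plan, after the chi-square sentence, add: *The difference in FP uptake between arms (intervention minus control) will be reported with a two-sided 95% confidence interval by a small-sample method such as Newcombe.*
2. Section 17.0, Sample Size Determination, replace the reliability and sufficiency wording with: *With 20 per arm, the 95% confidence interval half-width for the uptake difference is about 24 to 28 percentage points (assumed control uptake 25% to 50%, gain 0 to 45 points). The interval as well as the point estimate will inform any larger RCT.*
3. Optionally, after w=.45, add: *This corresponds to about 25% versus 70%, or 50% versus 91%, uptake.*

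The cost is two or three edits to the text and one interval calculation. The design, sample size and test do not change. The downside is a less favourable statement of precision than the present text gives.
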